4. PARTICIPANT ENTRY

4.1 PRE-RANDOMISATION EVALUATIONS Women replying to our adverts will be assessed for eligibility by questionnaire.

4.2 INCLUSION CRITERIA Pregnant women with gestational diabetes (women will be given the option to start the study between 6 weeks and 6 months post-delivery) or women who have given birth in the last 12 months and had gestational diabetes during that pregnancy, aged 18-45, access to a smartphone with an operating system of iOS 9.0 or above, or Android 5.0 or above [CB: operating systems correct as of 23/03/21]

4.3 EXCLUSION CRITERIA Diabetes outside of pregnancy (diagnosis of type 1 or 2 diabetes; or HbA1c 48 mmol/mol or above). Health contra-indications to moderate-vigorous exercise. Planning pregnancy during the study period or become pregnant during the study period. Cancer, kidney disease, liver disease, or pancreatitis. Have had gastric bypass surgery or similar weight loss surgery.

4.4 WITHDRAWAL CRITERIA If women withdraw consent or become pregnant during the study period, the data collected to that point will be retained, they will be withdrawn from the study and we will request permission to collect safety outcomes from them.

If they agree to participate, consent will be gained and stored in the site file.

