8.2 TRIAL CLOSURE

9. STATISTICS AND DATA ANALYSIS

10. MONITORING

GLOSSARY OF ABBREVIATIONS

RCT	Randomised Controlled Trial
GDM	Gestational Diabetes Mellitus

POST-GDM-DNA; Post-delivery intervention for weight loss, glycaemia and cardiovascular health

IRAS ID 292085

Protocol v12.1 8/3/22

CI	Chief investigator
TMG	Trial Management Group
GCP	Good clinical practice
HbA1c	Glycated haemoglobin - monitors average blood glucose
HDL	High-density lipoprotein cholesterol
LDL	Low-density lipoprotein cholesterol
BP	Blood pressure

KEYWORDS

Weight, blood pressure, glycaemia, HbA1c, physical activity, wearable, postnatal, post-delivery, DNA, personalised

STUDY SUMMARY

TITLE Post-delivery intervention in women with previous gestational diabetes mellitus for weight loss, glycaemia and cardiovascular health

DESIGN Feasibility study

Allocation: RCT

AIMS To determine the feasibility of a post-delivery intervention to improve glycemia and cardiovascular function and promote weight loss in women who have had gestational diabetes.

OUTCOME MEASURES Primary outcome; Effect of intervention on HbA1c: difference in HbA1c between intervention arm and control arm measured at 12 weeks.

Secondary Outcomes;

- Adherence to intervention;
- Willingness to be randomised to post-delivery intervention;
- Process measures to evaluate patient experience of study and intervention;
- Participants' preferred time to commence the study, within the start date allowance of 6 weeks – 6 month post-delivery.
- Between-arm differences and within-arm differences to evaluate:
 - Effect of intervention on HbA1c at 12 and 24 weeks
 - Effect of intervention on weight and BMI at 12 and 24 weeks
 - Effect of intervention on systolic and diastolic blood pressure at 12 and 24 weeks
 - Effect of intervention on lipid profile (total cholesterol, HDL, LDL) at 12 and 24 weeks
 - Effect of intervention on physical activity at 12 and 24 weeks

POPULATION We will recruit 50 women aged 18-45 with previous gestational diabetes and randomise them to 1 of 2 arms to commence study at 6 weeks – 6 months post-delivery. Women starting the study at 13 weeks post-delivery will have their routine post-delivery HbA1c act as baseline HBA1c.

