3. STUDY DESIGN

We will conduct a feasibility study for an open-label, randomised, controlled trial of a personalised post-delivery intervention (*DNA Nudge*) to improve weight, glycaemia and cardiovascular function in women with previous GDM.

The study is designed to be remote, to enable the study to begin and continue in the pandemic and minimise barriers to recruitment. Study participants will be provided with equipment and instructions to collect samples and measurements at home. Contact with the research team will be over telephone or Microsoft Teams video call.

We will advertise in diabetes antenatal clinics using word-of-mouth, posters, social media and on departmental emails at Imperial College Healthcare NHS Trust or Imperial College POST-GDM-DNA; Post-delivery intervention for weight loss, glycaemia and cardiovascular health IRAS ID 292085

for women with current/previous GDM aged 18-45. We will recruit via Twitter, email and in-person encounters.

We will randomise women to 1 of 2 arms:

Arm 1: Standard dietary and physical activity advice as per NICE guidelines at week 1 (active control arm; n = 25)

Arm 2: DNA-based personalised dietary and physical advice delivered by DNA Nudge dietician at week 1 and by DNA Nudge wearable and app for weeks 1-24 (intervention arm; n = 25)

Women not randomised to DNA Nudge will be provided with an activity app/wearable device (Fitbit) to monitor daily step count. All women will be provided with a home BP monitor and weighing scales.

Week 1

Eligibility assessment, consent, randomisation, IPAQ questionnaire, baseline BP and weight, blood sample collected for baseline lipid profile.

Some women will begin the study at 13 weeks post-delivery and coincide with the routine postnatal HbA1c for women with GDM. The routine post-delivery HbA1c will be baseline HbA1c for this study. For women who commence the study outside the 13 weeks post-delivery window, a finger prick blood sample will be used for a baseline HbA1c test.

Women in the control arm will be given standard dietary and physical activity advice by the research team, in line with NICE guidelines.

Women in the DNA Nudge arm will provide a cheek swab for DNA analysis, carried out by DNA Nudge. They will be given personalised dietary advice by a DNA Nudge dietician, and be provided with DNA Nudge wearable, app and instructions.

Week 6:

Telephone/video-call follow-up to check ongoing willingness to participate and assess adherence.

Week 12:

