11.2 CONSENT

Consent to enter the study must be sought from each participant only after a full explanation has been given, an information leaflet offered and time allowed for consideration. Signed participant consent should be obtained. The right of the participant to refuse to participate without giving reasons must be respected. After the participant has entered the study the clinician remains free to give alternative treatment to that specified in the protocol at any stage if he/she feels it is in the participant's best interest, but the reasons for doing so should be recorded. In these cases the participants remain within the study for the purposes of follow-up and data analysis. All participants are free to withdraw at any time from the protocol treatment without giving reasons and without prejudicing further treatment.

As this study follows a remote design, the informed consent process will be either face to face or using an online eConsent platform provided by REDCap.

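### Women who leave the study are asked for safety outcomes but not the 12-week HbA1c, and follow-up is not stated for a woman who herself stops the intervention

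*Combined protocol and SAP*

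**What the plan says.** The Study Summary defines the primary outcome as the "difference in HbA1c between intervention arm and control arm measured at 12 weeks".

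Section 4.4 (Withdrawal Criteria) has two triggers and keeps earlier data: "If women withdraw consent or become pregnant during the study period, the data collected to that point will be retained". For what follows, it says "they will be withdrawn from the study and we will request permission to collect safety outcomes from them".

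Section 11.2 (Consent) deals with treatment rather than study participation. It first says that "the clinician remains free to give alternative treatment to that specified in the protocol at any stage", and of those women: "In these cases the participants remain within the study for the purposes of follow-up and data analysis". The next sentence concerns the woman's own decision: "All participants are free to withdraw at any time from the protocol treatment without giving reasons and without prejudicing further treatment". It does not say whether she is followed afterwards.

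Section 3 describes the contacts at weeks 6 and 18 as "Telephone/video-call follow-up to check ongoing willingness to participate and assess adherence". The week-12 contact covers the same two topics and also collects the HbA1c and lipid sample.

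Section 8 gives 24 weeks as the length of follow-up. Section 8.1 takes women lost to follow-up out of the study. The Statistics and Data Analysis section names no analysis set and no rule for missing values.

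**The concern.** The plan already intends to ask a departing woman for permission to collect something further, but the request leaves out the endpoint on which the arms are compared. A value that was never collected cannot be recovered in the analysis.

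A second group has no stated path: women who stop using the app or wearable but have not refused further samples. Because the contacts take willingness and adherence together, one member of staff could record such a woman as a poor adherer and keep her in follow-up, while another could record her as withdrawn. If some are recorded as withdrawn, the 12-week comparison leans towards women who stayed engaged, and the randomised groups are no longer compared in full. With 25 women per arm, each missing woman is 1/25 = 4% of her arm.

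**Working it through.** **What each section covers**

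| Event | Where | Follow-up stated |
|---|---|---|
| Woman withdraws consent | 4.4 | Earlier data kept; permission sought for safety outcomes only |
| Woman becomes pregnant | 4.4 | Same |
| Clinician gives alternative treatment | 11.2 | Stays in follow-up and analysis |
| Woman herself leaves protocol treatment | 11.2 | Not stated |
| Woman lost to follow-up | 8.1 | Removed from the study |

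The follow-up promise in 11.2 opens by pointing back to the clinician's change of treatment, and it comes before the sentence on the woman's own choice. Read as written, it does not reach the fourth row. Nothing in section 8, 8.1 or the statistics section fills that row.

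**Timing.** Of the contacts at weeks 6, 12 and 18, only week 6 clearly precedes the primary measurement. Week 12 is the measurement contact itself. A departure at week 18 costs the 24-week value but not the primary one.

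**Size.** The plan gives 25 women per arm. It gives no loss rate, no SD for HbA1c and no expected difference between leavers and stayers, so there is no stated figure to reproduce and the following loss rates and gaps are assumptions.

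*Shift in the between-arm difference.* Suppose a share p of one arm is unmeasured, and the unmeasured women would have had a mean higher by d than the measured women, whose mean is m. The mean of the whole arm is (1 − p) × m + p × (m + d) = m + p × d, so the observed mean is too low by p × d.

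- 5 of 25 lost, p = 0.20, d = 0.5 SD: 0.20 × 0.5 = 0.10 SD.
- Low end, p = 0.10, d = 0.25 SD: 0.025 SD.
- High end, p = 0.30, d = 1 SD: 0.30 SD.

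These figures are for loss in one arm only. With loss in both arms, the net shift is the difference between the two products. Equal loss with an equal gap gives 0.10 − 0.10 = 0.

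*Precision.* The 95% CI half-width for a difference in means, in SD units, is t × √(2/n).

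- n = 25 per arm: 2.011 × √(2/25) = 0.57 SD.
- n = 20 per arm (5 lost in each): 2.024 × √(2/20) = 0.64 SD.

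With 1.96 in place of t, these become 0.55 and 0.62 SD. The widening occurs even when the losses are balanced and cause no shift.

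**The case against.** A reader might infer that the primary comparison necessarily loses every woman who stops the intervention. The documents do not say so. Section 4.4 is triggered by withdrawn consent or pregnancy, and no section makes giving up the device a ground for withdrawal. Adherence is itself an objective, checked during follow-up, and device usage data are collected at week 24. A design that measures adherence presumably expects to follow poor adherers. This stands. The text leaves the case open, and loss is a possibility rather than a rule.

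A reader might also infer that 4.4 and 11.2 contradict each other. They do not, because one covers leaving the study and the other a change of treatment. The fault is an event that falls between them.

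A third tempting inference is that the loss would fall mainly in the intervention arm and flatter it. Section 4.4 applies to both arms, controls also have a wearable (a Fitbit), and both arms record weight and blood pressure twice a week for 24 weeks. Only the intervention arm receives its dietary programme through a device and app over 24 weeks, so unequal loss is plausible in an open-label trial, but nothing in the documents establishes it or its direction.

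Two further points are fair. Asking for safety outcomes is not a defect, since it serves adverse event reporting. And this is a feasibility study sized on pilot guidance and evaluated largely by description, which lowers the stakes. It does not remove them, because the plan makes HbA1c at 12 weeks its primary outcome and intends a between-group comparison.

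**Conclusion.** The point holds as a gap in what will be collected. Followed exactly, 4.4 leaves a woman who withdraws consent or becomes pregnant before week 12 without a primary value, because only safety outcomes are sought. Section 11.2 leaves follow-up unstated for a woman who herself leaves protocol treatment, so she may be handled as withdrawn.

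A bias has not been demonstrated. The 0.10 SD shift rests on an assumed 20% loss in one arm, none in the other, and a 0.5 SD gap. The assumed range of 10–30% loss and 0.25–1 SD gap gives 0.025 to 0.30 SD. The widening from 0.57 to 0.64 SD rests on a different assumption, 5 women lost in each arm. The change is worth making because it is cheap and because the missing values cannot be obtained later.

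**What to change.** - In 4.4, separate (a) stopping the intervention or device from (b) withdrawing from data collection.
- State that women in (a) stay in follow-up for the week-12 and week-24 HbA1c and the other outcomes, and are analysed in the arm to which they were randomised. This gives the woman's own decision in 11.2 the follow-up already stated for a clinician's change of treatment.
- For women who withdraw consent, extend the permission request in 4.4 to the week-12 (and week-24) HbA1c sample. They remain free to refuse.
- At the existing week 6, 12 and 18 contacts, ask separately about continuing the intervention and continuing the samples.
- Report any HbA1c taken after a new pregnancy separately.
- Leave the grounds for withdrawal unchanged.

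The cost is wording in the protocol and information leaflet and a few extra home sample kits, with no new contacts. Some women will decline, so the change reduces the loss without removing it.

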5. RANDOMISATION AND ENROLMENT PROCEDURE

This will be an open-label trial. Randomisation will be in a 1:1 ratio by serially numbered, sealed, opaque envelopes, which will be prepared by a member of staff outside the research team.

Randomisation will be stratified by breastfeeding status (yes/no) at the time of recruitment.

5.1 RANDOMISATION OR REGISTRATION PRACTICALITIES Sealed envelopes will kept in a locked filing cabinet in a research office at Queen Charlotte's and Chelsea Hospital. Randomisation will occur in person at the QCCH site.

5.2 UNBLINDING This will be an open-label study. Data analysis will be study-arm blinded, unblinding will occur after completion.

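### The protocol does not fix when the breastfeeding stratum is read, and for women recruited in pregnancy, or well before a deferred start, the reading could be undefined or out of date

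*Combined protocol and SAP*

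**What the plan says.** Section 5 sets out the allocation: "Randomisation will be in a 1:1 ratio by serially numbered, sealed, opaque envelopes". It then gives the only stratification factor: "Randomisation will be stratified by breastfeeding status (yes/no) at the time of recruitment". There are two levels and no rule for a woman who has not yet delivered. No block size is stated.

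Section 4.2 describes two routes into the study. The first is "Pregnant women with gestational diabetes (women will be given the option to start the study between 6 weeks and 6 months post-delivery". The second is "women who have given birth in the last 12 months and had gestational diabetes during that pregnancy". Section 3 supports the antenatal route: "We will advertise in diabetes antenatal clinics using word-of-mouth, posters, social media".

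The Week 1 entry in section 3 reads "Eligibility assessment, consent, randomisation, IPAQ questionnaire, baseline BP and weight, blood sample collected for baseline lipid profile". The Study Summary, under Population, gives a sequence without defining its first step: "We will recruit 50 women aged 18-45 with previous gestational diabetes and randomise them to 1 of 2 arms to commence study".

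The visit lists in section 3 do not record breastfeeding at any visit. The statistics section (numbered 8 in the body) plans descriptive statistics and a between-group regression, and mentions neither the stratum nor any covariate.

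**The concern.** Breastfeeding is the one characteristic the sponsor chose to balance, in a trial of 25 women per arm. A stratum does this only if it is read when it has a meaningful value, close to the moment of allocation.

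The wording ties the reading to recruitment, and for some women recruitment may come before delivery. Such a woman has no feeding status for the index baby. Staff would have to enter no, guess, or wait until she starts, and the protocol does not say which. A woman recruited soon after birth who defers her start could also have changed status by then.

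If the early reading is used, one stratum would mix women who are breastfeeding at Week 1 with women who are not. The arms could then differ by chance on the factor the design meant to control. Because feeding status is not scheduled to be recorded at any visit and no adjustment is planned, the problem would be neither seen nor corrected later.

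**Working it through.** **Plan's own figure.** The only figure to reproduce is the sample size: 25 + 25 = 50, which agrees. It rests on pilot-study guidance, so there is no power calculation to check.

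**The sections side by side.**
- Section 5: status is read at recruitment.
- Section 4.2: a woman may enter by the pregnancy route and starts 6 weeks to 6 months after delivery.
- Section 3, Week 1: eligibility, consent and randomisation take place at study start, hence after delivery.
- Section 4.1: women who answer an advert are assessed for eligibility by questionnaire, which may be earlier than Week 1.

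Two readings follow. (a) Recruitment means consent and randomisation in Week 1; the stratum is then valid for everyone. (b) Recruitment means first identification or enrolment, possibly in pregnancy; the stratum is then undefined or possibly out of date for some women. The text does not choose between them.

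**Size under reading (b).** Inputs from the protocol: 50 women, 1:1 allocation, one two-level stratum. Assumptions not in the documents: permuted blocks of 4 within stratum; breastfeeding prevalence p at Week 1 of 30%, 50% or 70%; a share f recruited in pregnancy, all coded as no. The outcome is the between-arm difference in the proportion breastfeeding at Week 1. Ranges cover the three prevalences and are good to about one percentage point.

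| Share f recruited in pregnancy | SD of difference (points) | Chance of a gap of 20 points or more |
|---|---|---|
| 0% | about 3 | about 0% |
| 25% | 8-10 | 2-5% |
| 50% | 10-12 | 7-11% |
| 75% | 12-13 | 12-15% |
| 100% | 13-14 | 15-19% |

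Anyone repeating this should count gaps of exactly 20 points with a small numerical tolerance. Without it some are lost to rounding, and the last column below the first row becomes 2-3%, 6-10%, 10-14% and 12-16%.

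**Check of the last row.** At f = 100% the stratum does nothing, so the SD should be close to √(2p(1−p)/25). For p = 0.5 this is √(2 × 0.25/25) = √0.02 = 0.141. For p = 0.3 it is √(2 × 0.21/25) = √0.0168 = 0.130. Both match.

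**Exact limiting case.** Suppose all 50 women are recruited antenatally, exactly K breastfeed at Week 1 and 25 go to each arm. The number x in one arm has P(x) = C(K, x) × C(50−K, 25−x) / C(50, 25), and the gap in women is |2x − K|. The chance of a gap of at least 5 women (5/25 = 20 points) is 0.217, 0.148, 0.258, 0.148 and 0.217 for K = 15, 20, 25, 30 and 35. These values are uneven because 2x − K has the same parity as K: for K = 20 or 30, at least 5 in effect means at least 6. At a threshold of 6 the odd-K values fall to 0.06-0.09. The simulated ranges are the better guide, and this case is only an upper bound on the share.

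**The case against.** The strongest reply is that the schedule already answers the question. Consent and randomisation are listed together in Week 1, which is after delivery for every participant, and the Study Summary speaks of women with previous gestational diabetes. Staff stratifying a Week 1 allocation could simply ask then. On that reading nothing is wrong. This stands as far as it goes: the early reading is possible, not established, and no passage says a pregnant woman would be coded as no. It does not settle the matter, because section 5 does not refer to randomisation and recruitment is nowhere defined. The Study Summary also lists recruiting, randomising and commencing as successive steps.

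A reader might infer that the stratum is void for women recruited in pregnancy. The documents do not support that as a fact; it holds only if the status is actually taken before delivery.

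A reader might also infer that the stratification fails because it does not balance breastfeeding over the trial. No baseline stratum does that. It balances status when it is read; later feeding changes come after randomisation, and the fix proposed here would not balance them either.

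It is also fair to say that the consequence is limited. Women recruited after delivery are still stratified, allocation stays random, and this is a feasibility study with mainly descriptive analysis. The documents give no effect of breastfeeding on HbA1c, weight or lipids, so no distortion of the primary outcome is shown. No analysis by stratum is planned, so misclassification there is hypothetical.

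**Conclusion.** The point holds as an unresolved question of timing. Sections 3, 4.2 and 5 do not agree on when the stratum is read, and one permissible reading leaves it without a valid value for women recruited in pregnancy and possibly stale for women with a deferred start.

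On that reading the loss is chance balance, not bias. It runs from nothing if no one is recruited antenatally, through 2-5% and 7-11% at shares of a quarter and a half, to a 15-19% chance of a gap of 20 points or more if everyone is. That upper end equals having no stratification. These figures rest on assumed blocks of 4, assumed prevalence of 30-70% and the assumed coding of antenatal recruits as no. The near-zero figure under the Week 1 reading also depends on blocking, which the protocol does not state.

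Severity is minor and confidence moderate. No stated figure in the plan changes.

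**What to change.** - **Section 5:** replace the reference to the time of recruitment with wording such as: at randomisation in week 1, after delivery. This brings section 5 into line with the Week 1 schedule in section 3.
- **Week 1 procedures:** record breastfeeding status just before the envelope is opened.
- **Statistics section:** include this Week 1 stratum as a covariate in the between-arm comparison.

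The cost is one protocol sentence, one analysis sentence and one question at a contact that already takes place. No extra visit, staff or participants are needed.

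The change cannot alter the allocation of women already randomised. For them, report when the status was read, and use the status at Week 1 as the covariate where it can be established.

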8. STATISTICS AND DATA ANALYSIS

A study master list with patient identifiable information will be stored on a password-protected NHS computer in a locked research office at Queen Charlotte's and Chelsea Hospital, accessible only to the research team. This will match patient identifiable information with their study identification number. This study identification number will be used for the study database, which will be a cloud-based Excel database, which will be password protected and accessible only by the research team.

If any health conditions are discovered incidentally during the study they would be discussed with the participant immediately and their consent sought to share the information with their GP for the arrangement of their ongoing healthcare.

The study sample is 50 participants, 25 in each arm. The sample size has been based on guidance from the NIHR on pilot/feasibility studies (12) and the literature that it references that concludes that pilot studies should look for a sample size of at least 50 (13).

Data will be analysed after all participants have completed the 24 study weeks and all data is collected. Patient demographics will be presented as median/range or as categorical data where appropriate. We will evaluate primary and secondary outcomes using descriptive statistics. Between group comparison will be made using logistic regression.

Data and all appropriate documentation will be stored for 10 years after the completion of the study in accordance with ICHT guidance.

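### Randomisation is stratified by breastfeeding status but the analysis names no stratum term; if that status is prognostic and allocation is restricted within strata, the comparison is conservative and loses precision

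*Combined protocol and SAP*

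**What the plan says.** Section 5 (Randomisation and Enrolment Procedure) says: "Randomisation will be stratified by breastfeeding status (yes/no", with status taken at recruitment. On method it says only: "Randomisation will be in a 1:1 ratio by serially numbered, sealed, opaque envelopes". It gives no block size or other restriction within strata.

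The Study Summary defines the primary outcome as the "difference in HbA1c between intervention arm and control arm measured at 12 weeks", a continuous measure. It also lists between-arm differences in weight, blood pressure, lipids and physical activity.

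The section headed 8. Statistics and Data Analysis holds the whole analysis plan: "We will evaluate primary and secondary outcomes using descriptive statistics", followed by "Between group comparison will be made using logistic regression". It names no covariate, stratum term, significance level, sidedness or confidence interval. On size it says: "The study sample is 50 participants, 25 in each arm".

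**The concern.** Balancing the arms on a factor is worthwhile only if the factor is expected to predict outcome. When it does, and the balance is enforced, the design removes between-stratum variation from the treatment contrast. An analysis without the stratum leaves that variation in the residual, so the reported standard error exceeds the true one. The test then runs below its nominal level, and the precision that stratification was meant to buy is not reported. With 25 women per arm, precision is scarce, and the variable is already collected in order to randomise.

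**Working it through.** **Inputs from the documents.** Two strata (section 5); 1:1 allocation, restriction within strata not stated (section 5); 25 per arm (section 8, Statistics); continuous primary outcome (Study Summary); logistic regression as the only named model (section 8, Statistics).

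**Assumptions, none given in the documents.** The share R² of outcome variance explained by breastfeeding; blocks of 4 within strata; 50% of women breastfeeding; two-sided 5% tests.

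**The plan's own figure.** The sample size rests on literature that "concludes that pilot studies should look for a sample size of at least 50", with no effect size, SD, alpha or power. The only check possible is 25 + 25 = 50, which agrees. The plan offers no precision figure to reproduce.

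**Linear model, balance enforced within strata.** The unadjusted SE is proportional to 1 and the true SE to √(1 − R²). So:

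- excess width = 1/√(1 − R²) − 1
- actual level of a nominal 5% test = 2 × P(Z > 1.96/√(1 − R²))

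| Assumed R² | 1/√(1 − R²) | Excess width | Actual level |
|---|---|---|---|
| 5% | 1.026 | 2.6% | 4.4% |
| 10% | 1.054 | 5.4% | 3.9% |
| 15% | 1.085 | 8.5% | 3.4% |

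In SD units, the unadjusted 95% half-width is t(0.975, 48) × √(2/25) = 2.0106 × 0.2828 = 0.569. With the stratum it is 2.0117 × 0.2828 × √(1 − R²), which gives 0.555 at R² = 5% and 0.540 at 10%. The lost degree of freedom is negligible: at R² = 0 both half-widths are 0.569.

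A simulation (50 women, 20,000 runs) gave unadjusted type I error of 4.4% at R² = 5% and 3.7% at 10%. With the stratum term it stayed between 4.7% and 5.2% across R² from 0 to 30%.

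**Linear model, unrestricted 1:1 allocation.** Unadjusted type I error was 4.7% to 5.1% at every R² tried, so the test is valid. Adjustment then only adds precision: at R² = 10% the mean half-width fell from 0.572 to 0.549 SD.

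**Logistic model, blocks of 4** (about 8,000 runs; each cell is unadjusted / adjusted; power and mean estimate are at a true conditional log odds ratio of 1.0):

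| Assumed stratum log-OR | Half-width, no effect | Type I error | Power | Mean estimate |
|---|---|---|---|---|
| 0 | 1.134 / 1.148 | 4.4% / 5.3% | 39.0% / 41.6% | 1.04 / 1.07 |
| 1 | 1.133 / 1.191 | 3.7% / 4.9% | 35.9% / 40.2% | 0.98 / 1.08 |
| 2 | 1.131 / 1.325 | 2.5% / 4.4% | 23.8% / 31.9% | 0.82 / 1.09 |

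Here adjustment widens the interval. The cost of omission is an odds ratio that shrinks relative to the adjusted one, a conservative test and lower power. The first row, with no stratum effect, already shows a power gap of 2.6 points. That gap goes with the different small-sample levels of the two tests (4.4% and 5.3%), so not all of the 4.3-point gap in the second row comes from breastfeeding being prognostic.

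**The case against.** A reader might infer that the plan's confidence intervals are simply too wide. The documents do not support that, for four reasons.

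- **The direction depends on the model.** Excess width is a linear-model result. The plan names logistic regression, where adding the stratum makes the log-odds-ratio interval wider.
- **The restriction is not described.** Without blocks or a similar device inside strata, the unadjusted test keeps its level. Stratifying does normally imply some restriction, since otherwise it does nothing, and the plan fixes 25 per arm. The form of restriction is still missing, and it drives the figures.
- **Prognostic strength is unknown.** Nothing in the documents shows that breastfeeding predicts HbA1c. At R² of 0 to 10% the linear excess is 0 to about 5%.
- **No interval, alpha or test is specified.** The plan is mainly descriptive, and its silence on covariates is not an explicit commitment to an unadjusted analysis.

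All four stand as limits on size and certainty. They do not remove the omission. The plan commits to a regression comparison, has one stratification factor, and does not say that the factor will be used. Under either model, a prognostic stratum with enforced balance is better included.

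It can also be objected that the variable is not as ready to use as it looks. Section 5 takes breastfeeding status at recruitment, while section 4.2 admits women who are still pregnant, for whom that status is unclear. This also stands, and the fix must deal with it.

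**Conclusion.** The omission is certain; its size is conditional and modest. If breastfeeding is prognostic and allocation is restricted within strata, the comparison without the stratum is conservative. For a linear model of HbA1c, the loss is the 2.6% to 8.5% of interval width tabulated above for assumed R² of 5% to 15%. For the logistic model, it is attenuation and a few points of power at a moderate stratum effect. If allocation is unrestricted, only precision is at stake; if breastfeeding is not prognostic, nothing is.

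A reader might also infer that the trial risks false-positive findings. It does not, because the error runs in the conservative direction. The larger defect in the same sentence of the plan is that logistic regression does not directly estimate a difference in continuous HbA1c, and one revision should correct both.

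**What to change.** Add to the statistics section: *All between-arm comparisons include the breastfeeding stratum used for randomisation as a covariate.* For continuous outcomes such as 12-week HbA1c, apply this in a linear model rather than logistic regression, and report the between-arm difference with a 95% confidence interval.

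State in section 5 how allocation is restricted within strata. State also that the stratum value analysed is the one recorded at randomisation, and how it is assigned for women recruited while pregnant.

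The cost is a few lines of text and one degree of freedom, with no new data apart from a clear stratum record for women recruited in pregnancy.
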